5.5.1. Investigational Medicinal Product Return or Disposal

For additional information about study drug accountability, return, and disposal refer to Section 9.1.7.

6. STUDY PROCEDURES

The study procedures to be conducted for each subject enrolled in the study are presented in tabular form in [Appendix 2](#) and described in the text that follows. Additional details regarding urine collection procedures will be specified in the Laboratory Manual and Subject Procedures Manual.

Subject-reported outcomes will be administered, where available, and should be completed before any other study procedures. Invasive study procedures such as blood draws should be done at the end of a study visit, unless otherwise specified. Investigator questionnaires/assessments will be administered, where available, and should be performed prior to reviewing subject-reported outcomes for that visit, as much as possible.

The investigator must document any deviation from protocol procedures and notify the sponsor or contract research organization (CRO).

6.1. Subject Enrollment and Treatment Assignment

Subject eligibility will be established at the conclusion of the screening evaluations. The screening number and subject ID will be assigned for each subject by IWRS.

It is the responsibility of the investigator to ensure that each subject is eligible for the study before randomization. A subject will be considered enrolled once they have been randomized.

6.2. Pretreatment Assessments

6.2.1. Screening Visit

Subjects will be screened up to 35 days prior to randomization (Day 1) to determine eligibility for participation in the study. The Screening visit will take two separate days to complete. In addition, Screening Day 2 cannot occur earlier than 3 days after Screening Day 1 due to the timing of the morning urine voids and the 24 hour urine collection. Additional details regarding urine collection procedures will be specified in the Laboratory Manual and Subject Procedures Manual.

The following will be performed and documented at Screening:

- Obtain written informed consent
- [REDACTED]
- Obtain medical history, including a copy of the kidney biopsy pathology report with a histologic diagnosis of LMN performed within the 36 months prior to Screening. The report will be forwarded to the Gilead Medical Monitor for review and confirmation of eligibility prior to randomization on Day 1.

- Review inclusion and exclusion criteria
- Height and weight
- Complete PE
- Obtain urine samples for:
 - Urinary protein excretion will be determined using 2 consecutive morning voids as well as a 24-hour urine collection.
 - Urinalysis (with urine microscopy and spot protein-to-creatinine ratio). As contamination by menstrual blood may interfere with the primary endpoint, whether or not the patient is menstruating will be recorded on the CRF; microscopic urine examination will evaluate for active urine sediment (any of: > 5 WBC/hpf [pyuria], > 5 RBC/hpf [hematuria], or red cell casts in the absence of infection or other causes). In such circumstances, investigators may ask patients to return for another screening visit.
 - Urine biomarker sample
- Vital signs
- Standard 12-lead ECG
- Obtain blood samples for:
 - Clinical Laboratory Tests (hematology, serum chemistry, and coagulation)
 - HbA_{1c} and TSH
 - CRP and ESR
 - Autoantibody panel and complement levels
 - Serum Pregnancy Test (for females of childbearing potential) or FSH test (for females of nonchildbearing potential)
 - Virology Tests (HIV-1, HIV-2, HBV, and HCV)
 - HCV RNA VL (if subject is HCV Ab positive)
 - QuantiFERON[®] TB Gold in Tube Test (if applicable)
 - Biomarker Samples (whole blood TBNK biomarker sample, serum and plasma biomarker samples, vfPBMC sample, and PAXgene RNA sample)

- Chest x-ray (if one has not already been obtained within 3 months prior to screening)
- Record any serious adverse events and all adverse events related to protocol mandated procedures occurring after signing of the consent form
- Record any concomitant medication in the medical history

Subjects meeting all of the inclusion criteria and none of the exclusion criteria will return to the clinic within 35 days after screening for randomization into the study on Day 1.

Subjects who do not meet the eligibility criteria will be excluded from randomization and may be considered for rescreening one time for the study in consultation with the Sponsor or its designee. Refer to Section 4.4 for additional details.

A single retest of screening labs is permitted only if there is reason to believe the retest value will be within accepted parameters, or if the initial value was either due to a sample processing error or an extenuating circumstance.

From the time of obtaining informed consent through the first administration of investigational medicinal product, record all concomitant medication, serious adverse events (SAEs), as well as any adverse events related to protocol-mandated procedures on the adverse events case report form (eCRF). All other untoward medical occurrences observed during the screening period, including exacerbation or changes in medical history are to be captured on the medical history eCRF. See Section 7 Adverse Events and Toxicity Management for additional details.

6.2.2. Day 1 Baseline Assessments

[figure not shown]
The following will be performed and documented prior to dosing:

- Updates to medical history (if applicable)
- Review inclusion and exclusion criteria
- Weight
- Symptom-driven PE
- Obtain urine samples for:
 - Urinary protein excretion will be determined using 2 consecutive morning voids as well as a 24-hour urine collection. All 3 urine samples will be collected prior to Day 1, with the 24-hour urine collection as close to the Day 1 visit as possible.
 - Urinalysis (with urine microscopy and spot protein-to-creatinine ratio). As contamination by menstrual blood may interfere with the primary endpoint, whether or not the patient is menstruating will be recorded on the CRF; microscopic urine examination will evaluate for active urine sediment (any of: > 5 WBC/hpf [pyuria], > 5 RBC/hpf [hematuria], or red cell casts in the absence of infection or other causes).

- Urine pregnancy test (for females of childbearing potential)
- Urine biomarker sample
- SELENA-SLEDAI
- BILAG
- Patient Global Assessment of Disease activity
- Physician Global Assessment of Disease activity
- 36-Item Short Form Health Survey
- Vital signs
- Standard 12-lead ECG
- Obtain predose blood samples for:
 - Fasting Clinical Laboratory Tests (hematology, serum chemistry with lipid assessments, and coagulation)
 - CRP and ESR
 - Quantitative serum immunoglobulin test
 - Autoantibody panel and complement levels
 - HCV RNA VL (if subject was HCV Ab positive at Screening)
- Biomarker Samples (whole blood TBNK biomarker sample, serum and plasma biomarker samples, vfPBMC sample, and PAXgene RNA sample)
- Study drug dispensing
- Review and record all AEs and concomitant medications

Following the completion of the above assessments, the subject will be randomized and administered study drug.

CCI

6.3. Randomization

Subjects may not be randomized until the Gilead Medical Monitor has reviewed the kidney biopsy pathology report and has confirmed that a subject is eligible. Upon qualification for the study, subjects will be randomized in a 1:1 ratio using a computerized IWRS system.

For each subject at each visit, the clinic will contact the IWRS system and for the appropriate bottle number to be dispensed. The bottle will contain the relevant study drug for the period until the next dispensation visit.

Refer to Sections [3.3](#) and [6.1](#) for additional details.

6.4. Week 1 Assessments

- Weight
- Symptom-driven PE
- Obtain urine samples for:
 - Urinalysis (with urine microscopy and spot protein-to-creatinine ratio). As contamination by menstrual blood may interfere with the primary endpoint, whether or not the patient is menstruating will be recorded on the CRF; microscopic urine examination will evaluate for active urine sediment (any of: > 5 WBC/hpf [pyuria], > 5 RBC/hpf [hematuria], or red cell casts in the absence of infection or other causes).
 - Urine pregnancy test (for females of childbearing potential)
- Vital signs
- Obtain blood samples for:
 - Clinical Laboratory Tests (hematology, serum chemistry, and coagulation)
 - CRP and ESR
 - HCV RNA VL (if subject was HCV Ab positive at Screening)
- Study drug accountability
- Review and record all AEs and concomitant medications

6.5. Weeks 2 through Week 28 Assessments (excluding Week 16)

At Weeks 2, 4, and 20, subjects will be instructed to take their study drug in the clinic as the first study procedure prior to any others scheduled for those visits.

- Weight
- Symptom-driven PE

- Obtain urine samples for:
 - Urinalysis (with urine microscopy and spot protein-to-creatinine ratio). As contamination by menstrual blood may interfere with the primary endpoint, whether or not the patient is menstruating will be recorded on the CRF; microscopic urine examination will evaluate for active urine sediment (any of: > 5 WBC/hpf [pyuria], > 5 RBC/hpf [hematuria], or red cell casts in the absence of infection or other causes).
 - Urine pregnancy test (for females of childbearing potential)
 - Urine biomarker sample (Week 2 only)
- SELENA-SLEDAI
- Vital signs
- Obtain blood samples for:
 - Clinical Laboratory Tests (hematology, serum chemistry, and coagulation)
 - CRP and ESR
 - Quantitative serum immunoglobulin test (Weeks 8 and 24 only)
 - Autoantibody panel and complement levels (Weeks 2, 4, and 8 only)
 - HCV RNA VL (if subject was HCV Ab positive at Screening)
 - Plasma PK samples (Weeks 2, 4, and 20 [at least 30 minutes and up to 3 hours after dosing] and anytime at Weeks 8 and 24)
 - Biomarker Samples (Week 2 only [whole blood TBNK biomarker sample, serum and plasma biomarker samples, vFPBMC sample, and PAXgene RNA sample])
- Study drug accountability
- Study drug dispensing (Weeks 4, 8, 12, 20, 24, and 28 only)
- Review and record all AE and concomitant medications

6.6. Week 16 and Week 32 Assessments

At Weeks 16 and 32 subjects will be instructed to take their study drug after predose assessments have been completed (eg, up to 2 hours after PK sample collection). The following will be performed and documented prior to dosing:

- Weight
- Symptom-driven PE

- Obtain urine samples for:
 - For Week 16, subjects will submit 2 consecutive morning urine void samples to the study center approximately 7 days prior to the Week 16 visit to test their change in urinary protein excretion. Subjects will also submit a 24-hour urine collection that is collected immediately prior to the Week 16 visit, or as close to the Week 16 visit as possible. These results will inform their treatment assignment for the additional 16 weeks.
 - For Week 32, subjects will submit 2 consecutive morning urine void samples to the study center approximately 7 days prior to the Week 32 visit to test their change in urinary protein excretion. Subjects will also submit a 24-hour urine collection that is collected immediately prior to the Week 32 visit, or as close to the Week 32 visit as possible. These results will inform their treatment assignment for the additional 20 weeks in the Extended Blinded Treatment Phase.
 - Urinalysis (with urine microscopy and spot protein-to-creatinine ratio). As contamination by menstrual blood may interfere with the primary endpoint, whether or not the patient is menstruating will be recorded on the CRF; microscopic urine examination will evaluate for active urine sediment (any of: > 5 WBC/hpf [pyuria], > 5 RBC/hpf [hematuria], or red cell casts in the absence of infection or other causes).
 - Urine pregnancy test (for females of childbearing potential)
 - Urine PK sample (Week 16 only)
 - Urine biomarker sample
- SELENA-SLEDAI
- BILAG
- Patient Global Assessment of Disease activity
- Physician Global Assessment of Disease activity
- 36-Item Short Form Health Survey
- Vital signs
- Standard 12-lead ECG
- Obtain predose blood samples for:
 - Fasting Clinical Laboratory Tests (hematology, serum chemistry with lipid assessments, and coagulation)
 - CRP and ESR

- Autoantibody panel and complement levels
- HCV RNA VL (if subject was HCV Ab positive at Screening)
- Plasma PK sample (within 2 hours prior to dosing)
- Biomarker Samples (whole blood TBNK biomarker sample, serum and plasma biomarker samples, vfPBMC sample, and PAXgene RNA sample)
- Study drug accountability
- Study drug dispensing
- Review and record all AEs and concomitant medications

6.7. Week 36 through Week 48 Assessments

- Weight
- Symptom-driven PE
- Obtain urine samples for:
 - Urinalysis (with urine microscopy and spot protein-to-creatinine ratio). As contamination by menstrual blood may interfere with the primary endpoint, whether or not the patient is menstruating will be recorded on the CRF; microscopic urine examination will evaluate for active urine sediment (any of: > 5 WBC/hpf [pyuria], > 5 RBC/hpf [hematuria], or red cell casts in the absence of infection or other causes).
 - Urine pregnancy test (for females of childbearing potential)
- SELENA-SLEDAI
- Vital signs
- Obtain blood samples for:
 - Clinical Laboratory Tests (hematology, serum chemistry, and coagulation)
 - CRP and ESR
 - Quantitative serum immunoglobulin test (Week 48 only)
 - HCV RNA VL (if subject was HCV Ab positive at Screening)
- Study drug accountability

- Study drug dispensing
- Review and record all AEs and concomitant medications

6.8. Week 52 Assessments

- Weight
- Symptom-driven PE
- Obtain urine samples for:
 - Morning voids and 24-hour Urine Collection for Urine Protein. Urine samples from 3 consecutive days will be collected to evaluate urine protein, including morning voids during 2 consecutive days prior to each 24-hour urine collection (on the 3rd consecutive day).
 - Urinalysis (with urine microscopy and spot protein-to-creatinine ratio). As contamination by menstrual blood may interfere with the primary endpoint, whether or not the patient is menstruating will be recorded on the CRF; microscopic urine examination will evaluate for active urine sediment (any of: > 5 WBC/hpf [pyuria], > 5 RBC/hpf [hematuria], or red cell casts in the absence of infection or other causes).
 - Urine pregnancy test (for females of childbearing potential)
 - Urine biomarker sample
- SELENA-SLEDAI
- BILAG
- Patient Global Assessment of Disease activity
- Physician Global Assessment of Disease activity
- 36-Item Short Form Health Survey
- Vital signs
- Standard 12-lead ECG
- Obtain blood samples for:
 - Clinical Laboratory Tests (hematology, serum chemistry, and coagulation)
 - CRP and ESR

- Autoantibody panel and complement levels
- HCV RNA VL (if subject was HCV Ab positive at Screening)
- Biomarker Samples (whole blood TBNK biomarker sample, serum and plasma biomarker samples, vfPBMC sample, and PAXgene RNA sample)
- Study drug accountability
- Review and record all AEs and concomitant medications

6.9. Early Termination Assessments

All subjects who received at least one dose of study drug and discontinue the study early will have the below assessments completed at the time of study discontinuation:

- Weight
- Complete PE
- Obtain urine samples for:
 - Urine pregnancy test (for females of childbearing potential)
 - Urine biomarker sample
- Vital signs
- Standard 12-lead ECG
- Obtain blood samples for:
 - Clinical Laboratory Tests (hematology, serum chemistry, and coagulation)
 - CRP and ESR
 - Autoantibody panel and complement levels
 - HCV RNA VL (if subject was HCV Ab positive at Screening)
 - Biomarker Samples (whole blood TBNK biomarker sample, serum and plasma biomarker samples, vfPBMC sample, and PAXgene RNA sample)
- Study drug accountability
- Review and record all AEs and concomitant medications

6.10. Final Follow-Up Assessments (4 Weeks Post Treatment)

The following procedures will be completed 4 weeks (\pm 5 days) after the subject's last dose of study drug. Subjects that discontinue early from the study will be required to complete the FU visit.

- Weight
- Complete PE
- Obtain urine samples for:
 - Morning voids and 24-hour Urine Collection for Urine Protein. Urine samples from 3 consecutive days will be collected to evaluate urine protein, including morning voids during 2 consecutive days prior to each 24-hour urine collection (on the 3rd consecutive day).
 - Urine pregnancy test (for females of childbearing potential)
 - Urine biomarker sample
- SELENA-SLEDAI
- BILAG
- Patient Global Assessment of Disease activity
- Physician Global Assessment of Disease activity
- 36-Item Short Form Health Survey
- Vital signs
- Obtain blood samples for:
 - Fasting Clinical Laboratory Tests (hematology, serum chemistry with lipid assessments, and coagulation)
 - CRP and ESR
 - Autoantibody panel and complement levels
 - HCV RNA VL (if subject was HCV Ab positive at Screening)
 - Biomarker Samples (whole blood TBNK biomarker sample, serum and plasma biomarker samples, vfPBMC sample, and PAXgene RNA sample)
- Review and record all AEs and concomitant medications

6.11. Unscheduled Visit (exacerbation of LMN)

The following procedures will be completed at an unscheduled visit for exacerbation of LMN (worsening of proteinuria, and/or decrease in eGFR):

- Symptom-driven PE
- Obtain urine samples for:
 - Urinalysis (with urine microscopy and spot protein-to-creatinine ratio). As contamination by menstrual blood may interfere with the primary endpoint, whether or not the patient is menstruating will be recorded on the CRF; microscopic urine examination will evaluate for active urine sediment (any of: > 5 WBC/hpf [pyuria], > 5 RBC/hpf [hematuria], or red cell casts in the absence of infection or other causes).
 - Urine pregnancy test (for females of childbearing potential)
- Vital signs
- Review and record all AEs and concomitant medications

6.12. Study Assessments

6.12.1. Priority of Assessments

Subject-reported outcomes will be administered, where available, and are recommended to be completed before any other study procedures. Invasive study procedures such as blood draws should be done at the end of a study visit, unless otherwise specified. Investigator questionnaires/assessments will be administered, where available, and should be performed prior to reviewing subject-reported outcomes for that visit, as much as possible.

6.12.2. Efficacy

Efficacy assessments will be performed at the time points indicated in the study procedures table ([Appendix 2](#)).

6.12.2.1. Urine Protein Excretion

Several methods exist to assess urine protein excretion. Measurement of protein excretion in a 24-hour collection period has been the longstanding “gold standard” for the quantitative evaluation of proteinuria, and will be used to assess the primary outcome. An alternative method for quantitative evaluation of proteinuria is measurement of the ratio of protein to creatinine in an untimed “spot” urine specimen (UPCR). These ratios correct for variations in urinary concentration due to hydration and provide a more convenient method of assessing protein and albumin excretion than those requiring timed urine collections, and will be used to provide a preliminary assessment of response prior to the Week 16 and Week 32 visits.

6.12.2.2. Safety of Estrogens in Lupus Erythematosus National Assessment -Systemic Lupus Erythematosus Activity Index (SELENA-SLEDAI)

The SELENA-SLEDAI is an index of SLE flares commonly used in clinical trials as an assessment tool of SLE activity with scores that range from 0 to 105, with higher scores indicating more severe disease activity.

6.12.2.3. British Isles Lupus Activity Group (BILAG) Index

The BILAG is an index of SLE flares commonly used in clinical trials as an organ-specific assessment tool of SLE activity that includes a 97-question assessment based upon the evaluating physician's intent to treat, which requires an assessment of improved (1), the same (2), worse (3), or new (4) over the last month. Within each of 8 organ systems, multiple manifestations and laboratory tests are combined into a single score for that organ that range from A through E, with A representing very active disease and E indicating that the organ was never involved.

6.12.2.4. Physician's Global Assessments of Disease Activity

The Physician's Global Assessment of Disease Activity will be recorded on a 0 to 100 mm visual analogue scale (VAS; [Appendix 9](#)), with 0 indicating "no LMN disease activity" and 100 indicating "maximum LMN disease activity". It represents the average assessment of a patient's disease activity based on physical examination and laboratory data according to the evaluating physician.

6.12.2.5. Patient's Global Assessments of Disease Activity

The Patient Global Assessment reflects the patient's perceived overall health and disease activity, with disease activity estimated on a 0 to 100 mm visual analog scale.

6.12.2.6. 36-Item Short Form (SF) Healthy Survey (SF-36)

The SF-36 is a health related quality of life instrument consisting of 36 questions belonging to 8 domains in 2 components and covers a 4-week recall period:

- Physical well-being, 4 domains: physical functioning (10 items), role physical (4 items), bodily pain (2 items), and general health perceptions (5 items)
- Mental well-being, 4 domains: vitality (4 items), social functioning (2 items), role emotional (3 items), and mental health (5 items).
- The remaining item (health transition) is not part of the above domains but is kept separately. These scales will be rescaled from 0 to 100 (converting the lowest possible score to 0 and the highest possible score to 100), with higher scores indicating a better quality of life.

The SF-36 is not disease specific and has been validated in numerous health states.

6.12.3. Safety

Safety will be assessed via AEs, concomitant medications, physical examinations (complete and symptom-driven), vital signs, ECGs, and clinical laboratory results.

6.12.4. Clinical Laboratory Evaluations

All laboratory analyses will be performed at a central laboratory. Reference ranges will be supplied by the central laboratory and will be used by the investigator to assess the laboratory data for clinical significance and pathological changes.

Blood samples will be collected by venipuncture (**CCI** [REDACTED] in the arm at the time points indicated in the study procedures table ([Appendix 2](#)). In addition, urine samples for the clinical laboratory assessments will be collected. Subjects only need to be fasted on days where lipid profiling is scheduled.

- Refer to [Appendix 6](#) for table of clinical laboratory tests.

The laboratory values outside the normal range will be flagged and clinical relevance will be assessed by the investigator. More frequent sampling as well as additional tests may be performed as deemed necessary by the investigator as indicated.

Note that in the case where clinically significant laboratory test results are a potential reason for discontinuation from the study drug and withdrawal from the study, retesting of the affected parameter(s) should be prompt (within 3 to 7 days) after the investigator has consulted with the medical monitor. A decision regarding subject discontinuation should be made after the results from the retest are available (see Section [3.5](#) for additional information).

The details of sample handling and shipment instructions will be provided in a separate Laboratory Manual.

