After the screening period and randomization on Day 1, eligible subjects will enter the Blinded Treatment Phase and return to the study center at specified visits.

Blinded Treatment Phase

- Weeks 1, 2, 4, 8, 12, 16, 18, 20, 24, 28, and 32

Following completion of 16 weeks of dosing, the primary endpoint of the study will be evaluated in all subjects. To test their change in urinary protein excretion, subjects will submit 2 consecutive morning urine void samples to the study center approximately 7 days prior to the Week 16 visit. These results will inform their treatment assignment for the additional 16 weeks. Subjects who achieve a $\geq 35\%$ reduction in urinary protein excretion (using an average of the UPCR from 2 morning voids) from Baseline (Day 1) to Week 16 will continue to receive their assigned blinded study treatment (filgotinib

200 mg + PTM GS-9876 once daily; or GS-9876 30 mg + PTM filgotinib once daily) for an additional 16 weeks. Those subjects who do not achieve a $\geq 35\%$ reduction in urinary protein excretion from Baseline (Day 1) to Week 16 will switch study treatment for 16 weeks in a blinded fashion (ie, those on filgotinib 200 mg + PTM GS-9876 once daily will switch to GS-9876 30 mg + PTM filgotinib once daily, while those on GS-9876 30 mg + PTM filgotinib 200 mg once daily will switch to filgotinib 200 mg + PTM GS-9876 once daily). The primary outcome for urinary protein excretion will be determined using a 24-hour urine collection that is collected immediately prior to the Week 16 visit, or as close to the Week 16 visit as possible. Additional details regarding urine collection procedures will be specified in the Laboratory Manual and Subject Procedures Manual.

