After 32 weeks of blinded treatment, those who have received some benefit (a $\geq 35\%$ reduction in urinary protein excretion using an average of the UPCR from 2 morning voids from Day 1 [for subjects who remained on the randomized study treatment after Week 16] or from Week 16 [for subjects who switched treatment at Week 16]) will continue on their assigned blinded treatment for an additional 20 weeks in the Extended Blinded Treatment Phase. To test their change in urinary protein excretion, subjects will submit 2 consecutive morning urine void samples to the study center approximately 7 days prior to the Week 32 visit. These results will inform their treatment assignment for the additional 20 weeks in the Extended Blinded Treatment Phase. Subjects will also submit a 24-hour urine collection that is collected immediately prior to the Week 32 visit, or as close to the Week 32 visit as possible. Subjects who do not achieve a $\geq 35\%$ reduction in urinary protein excretion from Day 1 (for subjects who remained on the randomized study treatment after Week 16) or from Week 16 (for subjects who switched treatment at Week 16) to Week 32 will be allowed to continue whichever study treatment led to the greatest reduction in urinary protein excretion (from Day 1 to Week 16 on initial study treatment or from Week 16 to Week 32 on switched treatment), or either study treatment per the Investigator's discretion (eg, differences in tolerability or other non-renal benefits that support overriding the treatment assignment according to reduction in urinary protein excretion) during the Extended Blinded Treatment Phase.

Extended Blinded Treatment Phase

- Weeks 36, 40, 44, 48, and 52

All subjects who received at least one dose of study drug and discontinue the study early will complete an Early Termination (ET) visit at the time of study discontinuation.

All subjects, including those who terminate early from the study, will be required to complete a Final Follow-Up (FU) visit 4 weeks (\pm 5 days) after the last dose of study drug. For subjects that complete the entire study, the Final FU visit will be conducted at Week 56.

Screening Study Assessments:

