Appendix 6. Clinical Laboratory Assessment Table

Hematology	Chemistry	Urine	Other
White blood cell (WBC) count Hematocrit Hemoglobin Red blood cell (RBC) count Red blood cell indices Platelet count Differentials (absolute and percentage), including: Lymphocytes Monocytes Neutrophils Eosinophils Basophils Reticulocyte count	Alkaline phosphatase Aspartate aminotransferase (AST) Alanine aminotransferase (ALT) Gamma-glutamyl transpeptidase (GGT) Total bilirubin Direct and indirect bilirubin Total protein Albumin Bicarbonate Blood urea nitrogen (BUN) Calcium Chloride Creatinine Creatinine clearance ¹ Glucose Phosphorus Magnesium Potassium Sodium Creatine Phosphokinase (CPK) Amylase Lipase Uric acid (at screening only)	Appearance Blood Color Dipstick Glucose Specific gravity Nitrates Leukocyte esterase pH Protein Urobilinogen Reflex to microscopic urinalysis if dipstick result is abnormal. Spot urine protein and creatinine (for UPCR) 24-hour urine for protein and creatinine	QuantiFERON® TB – Gold In-Tube Analysis (if required per inclusion criteria; at screening only) FSH (as applicable; at screening only) HbA1c (at screening only) TSH (at screening only) C-reactive protein (CRP) Erythrocyte sedimentation rate (ESR) Quantitative immunoglobulins (IgG, IgM, and IgA) Autoantibody panel (ANA ² with reflex ENA ³ [dsDNA ⁴ , Sm ⁵ , RNP ⁶ , SSA, and SSB]) Complement levels (C3, C4, and CH50)
		Virology	
		Hepatitis B surface antigen (HBsAg) Hepatitis B virus (HBV) core antibody HBV DNA (reflex) Hepatitis C Virus (HCV) Ab (if positive, then reflex HCV RNA) HCV Viral Load (if applicable) Human immunodeficiency virus 1 and 2 Ab	
Coagulation	Fasting Lipids	Pregnancy	
Activated partial thromboplastin time (aPTT) Prothrombin time International normalized ratio (INR)	Total cholesterol Low-density lipoprotein (LDL) High-density lipoprotein (HDL) Triglycerides	In females of childbearing potential: Serum pregnancy test Urine pregnancy test	

Estimated glomerular filtration rate based on the MDRD formulation (eGFR_{MDRD})

ANA = antinuclear antibody

ENA = extractable nuclear antigen

dsDNA = double stranded DNA

Sm = Smith antigen

RNP = ribonucleoprotein

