7.2.2.1. Treatment-Emergent Laboratory Abnormalities

Treatment-emergent laboratory abnormalities are defined as values that increase at least 1 toxicity grade from baseline at any postbaseline time point, up to and including the date of last dose of study drug plus 30 days for subjects who permanently discontinued study drug. If the relevant baseline laboratory value is missing, any abnormality of at least Grade 1 observed within the time frame specified above will be considered treatment emergent.

The listing of all laboratory abnormalities will be provided.

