7.2.2.2. Summaries of Laboratory Abnormalities

The summaries (number and percentage of subjects) of treatment-emergent laboratory abnormalities will be provided by lab test; subjects will be categorized according to the most severe postbaseline abnormality grade for a given lab test.

For all summaries of laboratory abnormalities, the denominator is the number of subjects with nonmissing postbaseline values within study period.

A by-subject listing of treatment-emergent Grade 3 or 4 laboratory abnormalities will be provided by subject ID number and visit in chronological order. This listing will include all test results that were collected throughout the study for the lab test of interest, with all applicable severity grades displayed.

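### Fasting is not required at 14 of 17 later visits, yet the SAP grades glucose against a normally fasting baseline, so post-meal rises may enter the treatment-emergent high-glucose row

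*Protocol*

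**What the plan says.** Protocol Appendix 6 puts glucose in the chemistry column with no fasting qualifier ("Glucose Phosphorus Magnesium Potassium Sodium"). The procedures table (Protocol Appendix 2) has serum chemistry at every scheduled visit.

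At Day 1, Protocol 6.2.2 calls for "Fasting Clinical Laboratory Tests (hematology, serum chemistry with lipid assessments, and coagulation"). Sections 6.6 (Weeks 16 and 32) and 6.10 (Final Follow-Up) use the same words. At the remaining visits (Sections 6.4, 6.5, 6.7 and 6.8) the word fasting is dropped; Section 6.5, for example, asks for "Clinical Laboratory Tests (hematology, serum chemistry, and coagulation"). Section 6.12.4 gives the general rule: "Subjects only need to be fasted on days where lipid profiling is scheduled".

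On the analysis side, SAP 3.8.3 takes as baseline the last available value up to first dose, with an exception for analyses of an active treatment period. SAP 7.2.2 grades results by CTCAE v4.03. SAP 7.2.2.1 defines treatment-emergent abnormalities as "values that increase at least 1 toxicity grade from baseline at any postbaseline time point", and under SAP 7.2.2.2 "subjects will be categorized according to the most severe postbaseline abnormality grade for a given lab test". SAP 7.2 reports these by treatment period. Nothing in SAP 7.2 mentions fasting status. SAP 7.2.1 drops descriptive statistics for laboratory tests, which leaves this table as the only numeric laboratory summary.

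**The concern.** The reference value and most of the values compared with it are collected under different conditions. Baseline is normally a fasting sample; most later samples may or may not be. Keeping the worst grade means that one draw after a meal is enough to move a subject into the row. If meals raise glucose, the mismatch pushes the count in one direction only.

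What is at stake is the absolute incidence a reader sees. Both arms are active, so no placebo column shows the background rate, and means or medians that might reveal a visit pattern are not tabulated. Enrolment stopped at 9 subjects. If they split 4 and 5 (an assumption), one spurious case moves an arm's percentage by 1/5 = 20 or 1/4 = 25 points.

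**Working it through.** The plan states no visit count and no expected rate, so there is no figure of its own to reproduce.

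**Visit count.** The synopsis lists the Blinded Treatment Phase visits as "Weeks 1, 2, 4, 8, 12, 16, 18, 20, 24, 28, and 32", which is 11, and the Extended Blinded Treatment Phase visits as "Weeks 36, 40, 44, 48, and 52", which is 5. Final Follow-Up adds 1.

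- Later scheduled visits: 11 + 5 + 1 = 17
- Fasting chemistry specified after Day 1: Week 16, Week 32, Follow-Up = 3
- Fasting not required: 17 − 3 = 14

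| Period | Visits with chemistry | Fasting not required |
|---|---|---|
| Week 1 to Week 16 | 6 | 5 |
| Week 18 to Week 32 | 5 | 4 |
| Week 36 to Follow-Up | 6 | 5 |

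As extracted, Protocol Appendix 2 has the fasting-lipid mark under Early Termination rather than Follow-Up. Read that way the count is 15 of 17. Protocol 6.10 and SAP Appendix 1 both support Follow-Up, and the discrepancy may come from table extraction.

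**Baseline exception.** If a period analysis takes Week 16 or Week 32 as its reference, that draw is also fasting. The mismatch then recurs within the period.

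**Size, illustration 1.** Let p be the chance that a meal raises the grade at one visit where fasting is not required, with visits independent. The chance of at least one such rise over k visits is 1 − (1 − p)^k. All values of p are assumed.

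| p | k = 5 (before Week 16) | k = 14 (whole study) |
|---|---|---|
| 0% | 0% | 0% |
| 1% | 5% | 13% |
| 2% | 10% | 25% |
| 5% | 23% | 51% |
| 10% | 41% | 77% |

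**Size, illustration 2.** This is a simulation with no drug effect. Every input is an assumption: fasting mean 92 mg/dL, between-subject SD 8, within-subject SD 6, meal rise 10 to 20 mg/dL (SD 10 to 15), and 30% to 100% of the five draws at Weeks 1 to 12 taken fed. A subject is flagged if baseline is at or below the limit and any of the six draws to Week 16 exceeds it.

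| Assumed limit (mg/dL) | All six draws fasting | As scheduled |
|---|---|---|
| 105 | 19% | 45–88% |
| 110 | about 10% | 34–91% |
| 115 | 3.6% | 23–87% |
| 125 | 0.2% | 7–66% |
| 140 | under 0.1% | 0.5–24% |
| 160 | under 0.1% | 0–2% |

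The limit drives the result, and the documents do not give it.

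**The case against.** A reader might infer that the 14 draws are non-fasting and that the table will count meals as drug effect. The documents do not support either statement.

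- Section 6.12.4 says that fasting is not required on other days. It does not say that subjects ate. Fasting status at those visits is unknown.
- Treatment-emergent is a timing definition in this SAP, not an attribution. Both arms follow one blinded schedule, so any inflation should fall on both.
- The CTCAE glucose criteria are cited, not reproduced, so a fasting condition inside the scale cannot be ruled out. If there is one, the SAP still needs a rule for draws of unknown fasting status.
- The documents name no hyperglycaemia table. Glucose would be one row in a by-test summary. It is not an adverse event of interest (SAP 7.1.6) or a laboratory discontinuation criterion (Protocol 3.5.2).
- No laboratory testing is planned. SAP 7.2 lists every chemistry result by subject and visit, with out-of-range and graded values flagged. With 9 subjects a reader could trace a flagged glucose to its visit.

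These points stand. They limit the wording and the weight of the concern, and the listings soften its consequences. They do not supply the missing rule or make the summary table interpretable without the listings.

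**Conclusion.** The point holds as a gap in the analysis rule. Fasting is not required at 14 of 17 later visits (5 of 6 up to Week 16), and the SAP compares the worst grade with a normally fasting baseline without regard to fasting status. The high-glucose row may therefore include post-meal rises. Insofar as meals raise the assigned grade, the bias is upward.

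Its size cannot be stated. For Week 16, the simulation gives 23–91% of subjects flagged with assumed limits of 105 to 115 mg/dL and at most about 2% at 160 mg/dL. A flat statement that the table would show a high incidence is therefore not supported. No comparison between arms or hypothesis test is at risk. This is a cheap improvement to one row of a descriptive safety table.

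**What to change.** In SAP 7.2.2.1 and 7.2.2.2, present high glucose as two labelled rows:

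1. Draws at required-fasting visits (or with recorded fasting status, if available), graded against the fasting baseline for that period.
2. All other draws, labelled as fasting not required or unknown. These are graded and kept in the summary, but not read as a rise from a fasting baseline.

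Keep every value in the laboratory listings and in the Grade 3 or 4 listing.

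The cost is a few lines of SAP text and programming, with no new data. The downside is that the fasting row has about one draw per period. It has none on treatment after Week 32, because no visit from Week 36 to Week 52 requires fasting. Follow-Up is 4 weeks ± 5 days after last dose, so days 23 to 33; a draw on days 31 to 33 misses the 30-day window and would not count. For this reason the second row should be kept: restricting the table to fasting visits would remove all graded on-treatment glucose after Week 32 from the summary. The visit shows only that fasting was required, not that the subject complied, and the row label should say so.

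Separately, reconcile the fasting-lipid mark in Protocol Appendix 2 (Early Termination, as extracted) with Protocol 6.10 and SAP Appendix 1 (Follow-Up).
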